#### Data Collection and Analysis

Data collection will be performed with Research Electronic Data Capture (REDCap). Data will be analyzed with STATA 16 (StataCorp LLC; College Station, TX). Means and standard deviations will be used to understand general data trends. ANOVA will be used when comparing application methods. Regression analysis will be used to find associations with the speed of being able to complete the application process. Paired t-tests will be used to compare questionnaire scores at the final visit to the baseline visit. If the assumptions of these tests cannot be met, suitable alternative statistical tests (e.g., Kruskal-Wallis) will be used.

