**4. Randomization:** The investigator will access the online randomization tool (REDCap) and determine the order by which subjects will apply their lenses (*DMV inserter with an open end (A), DMV inserter with a closed end (B), three fingers (C), o-ring (D), tea light candle (E)*). Right eyes will undergo the application protocol; however, if the patient only needs a SL for their left eye, the left eye will undergo the protocol. Hand and eye dominance will be recorded. Subjects will then be instructed via training videos created by the investigators on how to do each application method. Each training video will be shown before starting each application method, and the examiner will answer the subject's questions prior to attempting the application method. The same investigator will teach each subject. Subjects will be timed during each application; however, time recording will not be made obvious. After a subject successfully completes an application method once for the designated eye, they will be asked to do the subsequent method. If a subject is unsuccessful with a method and declines to continue that method after being encouraged, the time will be recorded, and they will be allowed to try the next method. The subject will be allowed up to 15 minutes to complete each method. If the subject is unable to complete the method within that time frame, they will be instructed to do the next method to help avoid fatigue. If a patient stops a procedure before completing an application, this event will be recorded. Patients will be encouraged to try all five methods on the same day; however, subjects will be allowed to come back on a subsequent day if they get tired. Subjects will be asked to rank the ease of application for each method from easiest to most challenging after trying each method. If a subject needs a SL for their contralateral eye, they will be taught how to apply this lens after they have completed the training for their designated eye. If a subject is able to apply the lenses, they will be asked to remove the lenses as well. Only one removal method will be used (small plunger), and the removal time will also be timed for each method (timed separately from application).

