**5. SL Release:** After a subject completes the application and removal process, they will be given everything they need to wear the lenses (non-preserved saline (Adipack), application devices). They will also be given a trial bottle of Boston Simplus (contact lens care system), and they will be allowed to try their lenses for about one week. Subjects will be instructed to use their preferred application method at home.

**6. SL Adaptation Form:** Subjects will be given a take-home diary to complete during the one-week trial period. This diary will ask the subject about their experience with applying and removing their lenses, their comfort, and their perception of the SLs.

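### The five application methods are compared within subjects, but the plan names only an unspecified ANOVA and, as its one example fallback, Kruskal-Wallis, a test for independent groups

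*Combined protocol and SAP*

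**What the plan says.** Under Visit 2: Dispense Visit, step 4 (Randomization), the REDCap tool is used to "determine the order by which subjects will apply their lenses". What is randomised is the sequence of the five methods within a subject; nobody is allocated to a single method. Subjects are encouraged to attempt all five and each attempt is timed. Two outcomes follow, one time per method and a set of ranks: "Subjects will be asked to rank the ease of application for each method from easiest to most challenging after trying each method".

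Not every attempt will end in success. "The subject will be allowed up to 15 minutes to complete each method", and "If a subject is unsuccessful with a method and declines to continue that method after being encouraged, the time will be recorded".

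Under Data Collection and Analysis, the whole provision for comparing methods is "ANOVA will be used when comparing application methods". If test assumptions fail, "suitable alternative statistical tests (e.g., Kruskal-Wallis) will be used". The same paragraph does recognise pairing for another outcome: "Paired t-tests will be used to compare questionnaire scores at the final visit to the baseline visit".

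Hypothesis 1 (Specific Aims) concerns subjects' preference among the five methods. Step 5 of Visit 2 adds that "Subjects will be instructed to use their preferred application method at home", which suggests that each subject may also have one chosen method. The planned number is 25 subjects, plus five for screen failures. No alpha is stated.

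**The concern.** Five times or five ranks from one person are not five independent observations. Kruskal-Wallis, like one-way ANOVA, treats the 125 values (25 subjects × 5 methods) as if they came from five separate groups. The plan mentions no subject effect, repeated measures, mixed model or Friedman test. Because pairing is spelled out for the questionnaires, its absence for the methods stands out.

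The fallback could well be reached, since ranks are ordinal and times may be capped or stopped early. The consequence differs by outcome. Ranks within a subject always sum to the same total, so they are negatively correlated, and an independent-groups test rejects too often. Times within a subject are likely to be positively correlated, so such a test rejects too rarely and loses power.

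A second gap sits beside this one. The plan does not say whether preference in Hypothesis 1 means the ease ranks or one chosen method. If it is one choice per subject, the data are counts in five categories, and no test is named for them.

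**Working it through.** The plan states no power, alpha or effect size, so there is no figure of its own to reproduce. Inputs from the documents: n = 25 subjects, k = 5 methods. Assumed: alpha 0.05 and, for times only, the correlation and the effect.

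**Ease ranks, complete and untied.** Let SSB = n Σ(R̄ⱼ − 3)², where R̄ⱼ is the mean rank of method j.

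- Friedman: Q = 12/[k(k+1)] × SSB = (12/30) × SSB = 0.4 × SSB.
- Total sum of squares of the ranks: nk(k² − 1)/12 = 125 × 24/12 = 250.
- Tie-corrected Kruskal-Wallis: H = (nk − 1) × SSB/250 = (124/250) × SSB = 0.496 × SSB.
- Ratio: H/Q = 0.496/0.4 = 1.24, whatever the data.

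Both statistics are referred to chi-square with 4 df, critical value 9.488. H exceeds it whenever Q exceeds 9.488/1.24 = 7.652, and P(χ²₄ > 7.652) = 0.105. Simulation agrees: over 40,000 null trials Kruskal-Wallis rejected in 10.3% to 10.4% and Friedman in 4.7% to 4.8%; one-way ANOVA on the ranks rejected in about 10.9%. The result hardly depends on n (10.5% at 20, 10.6% at 30). This part needs no assumed effect or correlation.

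**Times.** The documents give no correlation between a subject's times, so a range is shown. Simulations used 25 subjects, exchangeable normal data with total variance 1, and one method shifted by 0.5 SD. For repeated-measures ANOVA the noncentrality is 25 × (4 × 0.1² + 0.4²)/(1 − ρ) = 5/(1 − ρ), referred to F(4, 96).

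| Correlation ρ | Kruskal-Wallis, type I error | Kruskal-Wallis, power | Friedman, power | One-way ANOVA, power | Repeated-measures ANOVA, power |
|---|---|---|---|---|---|
| 0 | 4.8% | 35% | 30% | 38% | 38% |
| 0.1 | 3.3% | 33% | 33% | 36% | 42% |
| 0.3 | 1.0% | 27% | 42% | 29% | 53% |
| 0.5 | 0.2% | 20% | 57% | 22% | 69% |
| 0.7 | 0.01% | 13% | 81% | 14% | 91% |

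On times there is no excess of false positives under the independent-groups tests. Friedman gains nothing over Kruskal-Wallis at a correlation of 0.1 or below, and much from 0.3 up. With about 19% of attempts capped and tied as worst, the pattern is the same: at correlation 0.5, Kruskal-Wallis 19% and Friedman 54%.

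**A limit on the remedy.** Repeated-measures ANOVA without a sphericity correction is not safe either. At correlation 0.5 and equal means, two simulation checks put its type I error at 7.4% and 7.7% with one method's SD doubled, and at 9.9% and 10.2% with it tripled (assumed values). A correction should therefore be part of the text.

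**The case against.** The strongest reply is that the plan has not committed to a wrong test. ANOVA is a family that includes the repeated-measures form, the fallback must be suitable, and Kruskal-Wallis is offered only as an example. That stands. A reader might infer that the trial will test Hypothesis 1 at twice the nominal error rate. The documents do not support this: it would take an analyst who uses the named fallback or a one-way ANOVA, ease ranks as the measure of preference, and an alpha of 0.05, and the plan states none of the three.

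A reader might also infer from the table that a stated aim loses power. It does not. Hypothesis 2 concerns the total time over all five methods, which is one value per subject and is assigned to regression. No hypothesis compares times between methods, so the figures on times matter only if the general sentence on comparing methods is applied to times.

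It can also be said that the study is preliminary. That limits the weight of any single p-value, but a small sample is no reason to name a test that does not fit the design, and the results are meant for publication and to guide patient education.

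Finally, one might want failed methods placed last by rule. For the ease ranks that would go too far. A failed method has still been tried, so the subject's own rank should exist and should not be overwritten with a tie.

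**Conclusion.** The point holds as a mismatch between design and named test: the only example fallback is of the wrong kind for five measurements on the same subject, and the ANOVA is left unspecified. The harm is conditional on how the paragraph is read.

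- If an independent-groups test is used on complete, untied ease ranks, the type I error is about 10.5% by Kruskal-Wallis, against about 4.7% by Friedman (n = 25, k = 5, assumed alpha 0.05). This touches Hypothesis 1 only if the ease ranks are the measure of preference.
- If it is used on times, the error is conservative. The size of the power loss depends on an unknown correlation; the 20% against 57% at a correlation of 0.5 is an illustration under an assumed 0.5 SD shift.

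Confidence is high in the mismatch and in the rank result, and lower in how much power would be lost on times. It should be fixed before analysis.

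**What to change.** In Data Collection and Analysis, replace the ANOVA sentence with:

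> Comparisons of application methods are within-subject. Subject-reported ease ranks will be compared with the Friedman test. Application times will be compared with a repeated-measures ANOVA with Greenhouse-Geisser correction, with the Friedman test as the fallback if its assumptions fail, including when times are capped at 15 minutes or stopped early; in the Friedman analysis of times, attempts not completed are tied as worst. Pairwise contrasts will be paired and adjusted for multiplicity.

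In the fallback sentence, give Friedman in place of Kruskal-Wallis as the example for method comparisons. Keep the ranks that subjects themselves give to methods they failed.

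State which outcome tests Hypothesis 1. If it is one chosen method per subject, record that choice at Visit 2 and use a one-sample goodness-of-fit test of equal proportions across the five methods. With 25 subjects, the chi-square version has an exact size of 4.6% at the 0.05 level.

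The cost is the rewording of one paragraph, slightly more analysis work and possibly one more recorded item. No subjects or visits are added. Friedman on times has slightly less power than Kruskal-Wallis if a subject's times are uncorrelated (about 30% against 35% in the assumed case).

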#### **STUDY TIMELINE**

|                    | 2020 | 2020 | 2020 | 2021 | 2021 | 2021 | 2021 | 2021 |
|--------------------|------|------|------|------|------|------|------|------|
|                    | Oct  | Nov  | Dec  | Jan  | Feb  | Mar  | Apr  | May  |
| Activity    |      |      |      |      |      |      |      |      |
| IRB Review         |      |      |      |      |      |      |      |      |
| Data Collection    |      |      |      |      |      |      |      |      |
| Data Analysis      |      |      |      |      |      |      |      |      |
| Final Study Report |      |      |      |      |      |      |      |      |

#### **PUBLICATION PLANS**

An abstract on application methods will be submitted for presentation at Academy 2021 Boston. A summary of this work will be submitted as a manuscript to *Contact Lens & Anterior Eye*.

#### **CONCLUSIONS**

This project will be the first to formally evaluate SL application methods in a randomized fashion, work that will help guide patient education and doctor prescribing. It may also lead to more patients becoming successful SL wearers by streamlining the overall SL fitting process.

